3.4.3 Efficacy assessments

Response Evaluation: Conventional response criteria are modeled after the 1999 International Working Group criteria for non-Hodgkin's lymphoma.³⁴ Disease sites that are considered non-measurable, such as malignant effusions, ascites, or bony lesions, will be considered in the overall response.

Complete Response: Complete disappearance of all detectable clinical and radiographic evidence of disease.

Nonspecific laboratory measures such as LDH or ESR are not included in the response assessment.

All lymph nodes and nodal masses must have regressed to normal size (< 1.5 cm in their greatest transverse diameter for nodes > 1.5 cm before therapy). Previously involved nodes that were 1.1 to 1.5 cm in greatest transverse diameter must have decreased to < 1 cm, or by > 75% in the sum of the products of the greatest diameters (SPD).

The spleen, if previously enlarged due to lymphoma, must have regressed in size and must not be palpable. Macroscopic nodules in any organs should no longer be present. Other organs considered to be enlarged before therapy due to lymphoma, such as liver and kidneys, must have decreased in size.

Negative bone marrow biopsy and aspirate, if bone marrow previously involved

Partial response (PR):

> 50% decrease in the sum of the products of greatest diameter (SPD) of the six largest (or fewer) dominant nodes or nodal masses. These nodes or masses should be a) clearly measurable in at least two perpendicular dimensions; b) be from as disparate regions of the body as possible; and c) include mediastinal and retroperitoneal areas of disease when involved.

Regression of splenic and hepatic nodules by > 50% in SPD

Bone marrow assessment is not relevant for determination of a PR

No sites of new or progressive disease

Stable disease (SD): less than a PR but is not progressive disease (see below), and must be maintained for a minimum of 4 weeks

Relapsed disease (after CR) / Progressive disease (after PR or SD)

Appearance of any new lesion or increase by > 50% in size of previously involved sites.

50% increase in greatest diameter of any previously identified node >1 cm in short axis, or in the SPD of more than one node

Standard Definitions of Disease and Survival Endpoints

Overall survival (OS) will be measured from registration to the time of death from any cause or last patient contact.

Event-free survival (EFS) is defined as the interval from registration to the date of first objective disease progression, death from any cause, or last patient evaluation. Patients who have not progressed or died will be censored at the last date they were assessed and deemed relapse-free.

Failure-free survival (FFS) is defined as the interval from registration to the date of first objective disease progression or last patient evaluation. Patients who have not progressed, or patients who have died without evidence of lymphoma progression, will be censored at the last date they were assessed and deemed progression- or relapse-free.

Time to tumor progression (TTP) is defined as the interval from the date the patient was last found to be progression-free, to the date of first objective disease progression.

3.4.4 Safety assessments

Safety assessments will consist of monitoring and recording adverse events that are grade 3 and above and all serious adverse events, the regular monitoring of hematology and blood chemistry values, regular measurement of vital signs and the performance of physical examinations.

These assessments should be performed within \pm 2 days of the scheduled day of assessment except for adverse events that will be evaluated continuously through the study. Toxicity will be scored using CTCAE Version 4.0 for toxicity and adverse event reporting. A copy of the CTCAE Version 4.0 can be downloaded from the CTEP homepage (<http://ctep.info.nih.gov>). All adverse clinical experiences, whether observed by the investigator or reported by the patient, must be recorded, with details about the duration and intensity of each episode, the action taken with respect to the test drug, and the patient's outcome. The investigator must evaluate each adverse experience for its relationship to the test drug and for its seriousness.

The investigator must appraise all abnormal laboratory results for their clinical significance. If any abnormal laboratory result is considered clinically significant, the investigator must provide details about the action taken with respect to the test drug and about the patient's outcome.

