3.2.5 Known Undesirable Side Effects of everolimus

Overall, safety data available from completed, controlled and uncontrolled studies indicate that everolimus is generally well tolerated at weekly or daily dose schedules. The safety profile is characterized by manageable adverse events (AEs). These AEs are generally reversible and non-cumulative.

Adverse events most frequently observed with everolimus are stomatitis, rash, diarrhea, fatigue, infections, asthenia, nausea, peripheral edema, decreased appetite, headache, dysgeusia, epistaxis, mucosal inflammation, pneumonitis, weight decreased, vomiting, pruritus, cough, dyspnea, dry skin, nail disorder, and pyrexia. Overall, the most frequently observed laboratory abnormalities include decreased hematologic parameters including hemoglobin, lymphocytes, platelets, and neutrophils (or collectively as pancytopenia); increased clinical chemistry parameters including cholesterol, triglycerides, glucose, aspartate transaminases, creatinine, alanine transaminases, and bilirubin; and decreased clinical chemistry parameters including phosphate and potassium. The majority of these AEs have been of mild to moderate severity (NCI CTC grade 1-2).

Everolimus has immunosuppressive properties and may predispose patients to bacterial, fungal, viral or protozoan infections, including infections with opportunistic pathogens. Localized and systemic infections, including pneumonia, other bacterial infections, invasive fungal infections, such as aspergillosis or candidiasis and viral infections including reactivation of hepatitis B virus, have been described in patients taking everolimus. Some of these infections have been severe (e.g. leading to sepsis, respiratory or hepatic failure) and occasionally have had a fatal outcome.

Physicians and patients should be aware of the increased risk of infection with everolimus. Treat pre-existing infections prior to starting treatment with everolimus. While taking everolimus, be vigilant for symptoms and signs of infection; if a diagnosis of infection is made, institute appropriate treatment promptly and consider interruption or discontinuation of everolimus. If a diagnosis of invasive systemic fungal infection is made, discontinue everolimus and treat with appropriate antifungal therapy.

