3.4.4.1 Adverse Events

Information about adverse events that are grade 3 or above, whether volunteered by the subject, discovered by investigator questioning, or detected through physical examination, laboratory test or other means, will be collected and recorded and followed as appropriate.

An adverse event is the appearance or worsening of any undesirable sign, symptom, or medical condition occurring after starting the study drug even if the event is not considered to be related to study drug. Medical conditions/diseases present before starting study drug are only considered adverse events if they worsen after starting study drug. Abnormal

laboratory values or test results constitute adverse events only if they induce clinical signs or symptoms, are considered clinically significant, or require therapy.

The occurrence of adverse events should be sought by non-directive questioning of the patient at each visit during the study. Adverse events also may be detected when they are volunteered by the patient during or between visits or through physical examination, laboratory test, or other assessments. As far as possible, each adverse event should be evaluated to determine:

1. the severity grade (mild, moderate, severe) or (grade 1-4) its relationship to the study drug(s) (suspected/not suspected)
2. its duration (start and end dates or if continuing at final exam)
3. action taken (no action taken; study drug dosage adjusted/temporarily interrupted; study drug permanently discontinued due to this adverse event; concomitant medication taken; non-drug therapy given; hospitalization/prolonged hospitalization)
4. whether it constitutes a serious adverse event (SAE)

All adverse events should be treated appropriately. Such treatment may include changes in study drug treatment including possible interruption or discontinuation, starting or stopping concomitant treatments, changes in the frequency or nature of assessments, hospitalization, or any other medically required intervention. Once an adverse event is detected, it should be followed until its resolution, and assessment should be made at each visit (or more frequently, if necessary) of any changes in severity, the suspected relationship to the study drug, the interventions required to treat it, and the outcome.

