1-yr EFS	Prob Stop for Futility	Avg N	Est 1- yr PFS	Lo 95% Post Int'l	Hi 95% Post Int'l	Prob H0 Rejected
0.45	0.60	40.3	0.42	0.25	0.58	0.03
0.5	0.37	47.7	0.47	0.25	0.62	0.12
0.55	0.17	54.1	0.53	0.35	0.67	0.28
0.60	0.07	57.5	0.59	0.40	0.72	0.57
0.65	0.02	59.1	0.64	0.50	0.77	0.83
0.70	0.01	59.8	0.70	0.58	0.82	0.96

Analysis of primary objective:

The proportion of patients positive for the toxicity evaluation as defined for this study: patients for which the minimum 2.5 mg everolimus every other day was not tolerable or any unexpected hospitalizations during protocol participation will be reported with an exact binomial calculation and 95% confidence interval. The proportion of patients requiring dose adjustments down as well as the proportion requiring dose adjustments up will be reported separately with confidence intervals. All other grade 1 and 2 toxicities will be reported by type and grade, overall and within intervals throughout the study (0, 60], (60, 90], (90,120], (120, 180], (180, 365] and (365, 1460].

Analysis of secondary objectives:

Standard life table methods will be used to analyze EFS. We will report the one and three-year EFS with 95% confidence intervals. The three-year EFS will be compared to the null EFS of 49% with a Z-score and a one-sided alpha level of 0.05.

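### The adverse-event recording rules conflict, which leaves the planned grade 1-2 tables on uncertain data; separately, the grade 3 or higher proportion behind the primary objective and N = 60 is missing from the analysis list

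*Combined protocol and SAP*

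**What the plan says.** On recording, the protocol gives two rules.

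- Narrow rule. Section 3.4.4 begins: "Safety assessments will consist of monitoring and recording adverse events that are grade 3 and above and all serious adverse events". Section 3.4.4.1 begins with the same threshold: "Information about adverse events that are grade 3 or above" is what will be collected and followed.
- Broad rule. Later in Section 3.4.4: "All adverse clinical experiences, whether observed by the investigator or reported by the patient, must be recorded", with duration, intensity, action taken and outcome. Section 3.4.4.1 defines an adverse event without any grade threshold, asks for open questioning at every visit, and asks that each event be graded from 1 to 4 where possible.

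On analysis, Section 6.0 (Analysis of primary objective) lists three things. The first is an exact binomial estimate, with 95% confidence interval, of the proportion of patients who cannot tolerate the stated minimum everolimus dose or who have an unexpected hospitalization. The second is the proportions needing dose changes down and up. The third is low-grade toxicity: "All other grade 1 and 2 toxicities will be reported by type and grade, overall and within intervals throughout the study", in six intervals from day 0 to day 1460.

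On the objective, Section 2.0 measures safety by how far grade III or higher CTCAE v4.0 toxicity is avoided. Section 6.0 (Sample size/Accrual Rate) justifies 60 patients by the precision, ±13%, with which the grade 3 or higher proportion can be estimated.

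**The concern.** There are two problems, and they are separate.

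First, a site that follows the opening sentence of either safety section would not enter non-serious grade 1-2 events, yet the analysis plan tabulates exactly those events. A reader of the final tables could not tell a low rate from a low rate of recording. The class is not small: Section 3.2.5 says that most everolimus adverse events seen in earlier studies were grade 1-2. Some of these events also bear on treatment. Addendum 5 links grade 2 stomatitis to dose interruption, and Addendum 7 has grade 2 pneumonitis prompt consideration of it. Under the narrow rule the event behind such a change need not appear in the adverse-event record.

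Second, the quantity that defines the primary objective and justifies the sample size has no line in the analysis list. The listed primary analysis concerns a different event, and the only toxicity report by type is for grades 1 and 2. At stake is whether the trial's report answers the question that the trial was sized to answer.

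**Working it through.** **1. The plan's own precision figure.** The input is n = 60 (Section 6.0). The plan does not state the proportion assumed, so I take p = 0.5, which gives the widest interval.

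- Normal approximation: half-width = 1.96 × √(0.5 × 0.5 / 60) = 1.96 × 0.0645 = 0.1265, or 12.7%.
- Exact (Clopper-Pearson) for 30/60: 36.8% to 63.2%, half-width 13.2%.

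Both round to 13%, so the stated figure reproduces. It refers to grade 3 or higher toxicity and is the same under either recording rule.

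**2. What the missing line would show.** Exact 95% intervals for n = 60 at illustrative counts (assumptions, not predictions):

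| Patients with grade 3+ | Proportion | Exact 95% CI |
|---|---|---|
| 6 | 10% | 3.8% to 20.5% |
| 12 | 20% | 10.8% to 32.3% |
| 18 | 30% | 18.8% to 43.2% |
| 30 | 50% | 36.8% to 63.2% |

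**3. Which results depend on the recording rule.**

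| Result | Data needed | Narrow rule | Broad rule |
|---|---|---|---|
| Grade 3+ proportion (Sections 2.0 and 6.0) | Grade 3+ events | Recorded | Recorded |
| Serious adverse events | All SAEs | Recorded | Recorded |
| Primary binomial estimate and safety stopping rule | Dose intolerance or unexpected hospitalization | Not a grade 1-2 count | Not a grade 1-2 count |
| Grade 1-2 tables by type and interval | Non-serious grade 1-2 events | Not recorded as events | Recorded |

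Only the last row changes.

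**4. Can scheduled tests fill that row?** In part. Section 3.2.5 lists blood counts, lipids, glucose, creatinine and transaminases among the common abnormalities, and Section 3.4.1 schedules tests from which these could be graded. There are three limits.

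- Stomatitis, rash, fatigue, diarrhea and nausea, also listed as frequent, have no scheduled test.
- Section 3.4.4.1 counts a laboratory abnormality as an adverse event only if it causes symptoms, is judged clinically significant or needs treatment.
- The last interval, (365, 1460], spans 1460 − 365 = 1095 days. By Section 3.4.1, scheduled chemistry and lipids stop at one year and so cover none of it. Blood counts stop at three years (day 1095) and cover 1095 − 365 = 730 of those days.

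**5. Size of the shortfall.** The documents give no expected grade 1-2 rate for this combination after high-dose therapy, so no figure can be put on it. The statement in Section 3.2.5 is about everolimus in general.

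**The case against.** The best defence is that the protocol does require low-grade data. The sentence requiring all adverse experiences to be recorded is mandatory, the adverse-event definition has no grade floor, and the grading scale starts at 1. This stands. A reader might infer that collection is limited to grade 3 and above, so that the tables rest on data nobody was asked to collect. The documents do not support that reading. They contain both rules, and the defect is the contradiction.

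A reader might also infer that the trial will understate toxicity. That goes too far. Any understatement depends on sites following the narrow rule, and it is then confined to descriptive grade 1-2 tables. Nor does the recording rule change from one interval to the next, so it does not by itself make intervals non-comparable. Only the laboratory-derived grades lose coverage, in the last interval.

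The dose consequences of low-grade events are not wholly lost either: Section 3.3.3 records dosages given, and Section 6.0 reports dose changes up and down.

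On the second problem, it can be said that the sample-size text already shows the intent to estimate the grade 3 or higher proportion, and that the word "other" in "All other grade 1 and 2 toxicities will be reported by type and grade" suggests higher grades were meant to be reported somewhere. That is fair as to intent, but no sentence in the analysis list does it. It can also be said that this is a separate matter from the recording rule. It is, and it is treated as such here.

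**Conclusion.** Both parts hold, within limits.

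The missing grade 3 or higher analysis is the weightier part and holds under either recording rule. The stated primary safety measure, and the only precision claim for safety (±13% at n = 60, reproduced as 12.7% to 13.2% at an assumed proportion of 50%), have no matching line in the analysis list. This does not mean that the trial cannot answer its question: the data are collected under both rules, and only the analysis text is missing.

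The recording conflict is a real contradiction with a narrower effect. Assuming sites follow the narrow rule, the grade 1-2 tables will omit non-serious clinical events, apart from laboratory grades derived from scheduled tests, and will understate low-grade clinical toxicity by an amount that the documents do not allow one to calculate. Assuming sites follow the broad rule, the tables are supported. No figure in the plan changes in either case.

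**What to change.** 1. In Section 6.0 (Analysis of primary objective), add the proportion of patients with any grade 3 or higher CTCAE v4.0 toxicity, with an exact 95% confidence interval, and a table of grade 3 or higher events by type. State how grade 3 or higher laboratory values that do not meet the adverse-event definition in Section 3.4.4.1 are counted. The cost is a few lines of text and no new collection of adverse events.

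2. Reconcile Sections 3.4.4 and 3.4.4.1 to one recording rule and align Section 6.0 and the case report form with it. Either option would do.

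   - Record all grades during treatment and keep the grade 1-2 tables, restricted to the period in which all grades are recorded. The cost is more data entry. Section 3.2.5 and Addendum 8 refer to patients treated before the February 2014 version was approved, and the current version is dated May 2018. If earlier patients were recorded under the narrow rule, ascertainment will be mixed unless their charts are reviewed, and the report should say so.
   - Keep grade 3 and above plus serious events, add any lower-grade event linked to a hold or dose change, and drop the grade 1-2 tables or limit them to laboratory grades derived from scheduled tests. The cost is mainly wording; the price is no table of low-grade clinical toxicity.

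These changes concern data capture and reporting only. They leave the dose-management rules as they are.

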3.4.4.1 Adverse Events

Information about adverse events that are grade 3 or above, whether volunteered by the subject, discovered by investigator questioning, or detected through physical examination, laboratory test or other means, will be collected and recorded and followed as appropriate.

An adverse event is the appearance or worsening of any undesirable sign, symptom, or medical condition occurring after starting the study drug even if the event is not considered to be related to study drug. Medical conditions/diseases present before starting study drug are only considered adverse events if they worsen after starting study drug. Abnormal

laboratory values or test results constitute adverse events only if they induce clinical signs or symptoms, are considered clinically significant, or require therapy.

The occurrence of adverse events should be sought by non-directive questioning of the patient at each visit during the study. Adverse events also may be detected when they are volunteered by the patient during or between visits or through physical examination, laboratory test, or other assessments. As far as possible, each adverse event should be evaluated to determine:

1. the severity grade (mild, moderate, severe) or (grade 1-4) its relationship to the study drug(s) (suspected/not suspected)
2. its duration (start and end dates or if continuing at final exam)
3. action taken (no action taken; study drug dosage adjusted/temporarily interrupted; study drug permanently discontinued due to this adverse event; concomitant medication taken; non-drug therapy given; hospitalization/prolonged hospitalization)
4. whether it constitutes a serious adverse event (SAE)

All adverse events should be treated appropriately. Such treatment may include changes in study drug treatment including possible interruption or discontinuation, starting or stopping concomitant treatments, changes in the frequency or nature of assessments, hospitalization, or any other medically required intervention. Once an adverse event is detected, it should be followed until its resolution, and assessment should be made at each visit (or more frequently, if necessary) of any changes in severity, the suspected relationship to the study drug, the interventions required to treat it, and the outcome.

Information about common side effects already known about the investigational drug can be found in the Investigators' Brochure. This information should be included in the patient informed consent and should be discussed with the patient during the study as needed.

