Clinical Experience of Everolimus in lymphoma: everolimus, an oral mTOR inhibitor, was tested at 10 mg qd in a Phase II study for patients with a number of different types of relapsed or refractory lymphomas – including aggressive, indolent and uncommon lymphomas^{32,33} . Thirty-seven (37) patients were treated in the aggressive lymphoma group - 20 (54%) with diffuse large B-cell (DLBC), 14 (38%) with MCL, 2 high grade, and 1 follicular grade III. Patients were eligible to enter if they had measurable disease and had met the following hematologic parameters: ANC \geq 1.0 x 109/L, platelets \geq 75.0 x 109/L and hemoglobin \geq 8 g/L. The median age was 72 years (range, 45-92). Patients had previously received a median of 4 prior therapies (range, 1-15). Prior stem cell transplant was allowed. The median treatment duration with Everolimus was 2 cycles (range 1-16+). The overall response rate was 32% (12/37; 95% CI: 20-49%) with 1 complete response and 11 partial responses. The overall response rate in the MCL patients was 29% (4/14); including one who received Everolimus for more than 14 cycles, while maintaining PR. The median time to progression for all 37 patients was 3.7 months (95% CI: 2.1 - 8.7). The median duration of response for the 12 responders was 5.5 months (95% CI: 2.3 - 9.2). Three patients are currently maintaining a response with a median of 10.5 months (2.9-15.6+ months). Everolimus was well tolerated. The incidence of grade 3 anemia, neutropenia, and thrombocytopenia in this heavily pretreated patient population was 11%, 16%, and 30%, respectively. Two patients developed grade 4 neutropenia. Grade 2 hypercholesterolemia occurred in 11%; grade 2 hyperglycemia in 16%; grade 3 hyperglycemia in 11% of the patients. One patient had grade 4 hypertriglyceridemia.

In the treatment of relapsed Hodgkin's disease, everolimus dosed at 10mg daily on a monthly cycle, the ORR was 47%. Ten of 19 patients had dose reductions or treatment delays. The median number of cycles at 10mg daily was five (range 1-20).

Everolimus serum levels are commercially available

- Quest Diagnostics (18883X) CPT code 80299, Mon-Fri
- Target trough concentrations 3-15 ng/mL

1.2 Hopkins experience of high-dose consolidative therapy with low grade B cell and Hodgkin's lymphoma.

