Hodgkin's data: Rituximab, high dose cy, and GM-CSF based immunotherapy for relapsed Hodgkin's lymphoma: This phase I/II, single-institution trial for relapsed classical Hodgkin lymphoma has just completed accrual of its planned 30 patients. Clinical outcomes of this platform, which was developed as a potentially less toxic alternative to autologous BMT, are encouraging. In the first 25 patients, whose median time between first-line therapy completion and relapse was 12 months, actuarial event-free survival is 79% at 1 year and 63% at 2 and 3 years following high-dose cyclophosphamide; overall survival is 100% at 2 years and 92% at 3 years. These early results are comparable to what is seen with autologous BMT. The toxicity profile has been manageable, and there has been no treatment-related mortality. Median time to neutrophil recovery after high dose cyclophosphamide was 17 days, and 21 days for platelet recovery with 5 patients not

requiring platelet transfusion. The trial was presented in a poster session at the 52nd American Society of Hematology annual meeting (Kasamon Y et al, *Blood* 2010, abstract 3954).

2.0 Primary Study Objective:

To determine the safety of maintenance rituximab and prolonged mTOR inhibition with everolimus in CD20+, B cell lymphomas, Gray Zone Lymphoma, and Hodgkin's Lymphoma after high-dose consolidative therapy.

- Safety will be determined by the extent of avoidance of \geq grade III common toxicities (CTCAE version 4.0)

2.1 Secondary Objectives:

- 1) The secondary endpoint of this study is to evaluate event free survival (EFS) at three years based on histology.
 - EFS will be histology grade specific: Mantle cell lymphoma group, low-grade lymphoma group, high-grade lymphoma group
- 2) To determine whether maintenance rituximab with everolimus treatment reduces the frequency of circulating cancer cells.
- 3) To determine if relapsed disease is sensitive, in-vivo, to mTor kinase inhibition.

3 Investigational plan

3.1 Overall study design: After high dose consolidative therapy, patient will receive one year of adjuvant rituximab and everolimus. Treatment evaluation with radiographs, standard laboratories and examination will follow for the next three years. Survival/disease status will also be assessed for an additional two years, for up to 5 years total of follow-up.

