 - Platelets $< 50,000$: hold drug until platelet count is $>75,000$ and restart at a dose level -2.5mg/day. Lowest dose allowed is 2.5mg every 4 days

- Platelets <10,000: transfuse PLT: when platelet count is >75,000 (transfusion independent: at least 7 days). Restart at a dose level -2.5mg/day; lowest dose allowed is 2.5mg every 4 days
- Neutropenia:
 - ANC <1,000/mm³ hold drug (and rituximab) until ANC >1,500 and restart at a dose level -2.5mg/day. Lowest dose allowed is 2.5mg every 4 days
 - No adjustments will be made for lymphopenia
- Lowest dose allowed on protocol is 2.5mg every 4 days. If serum concentrations on this dosing schedule are >15ng/mL or if on this dosing schedule greater than grade II toxicities are experienced the patient will be taken off study. However, patients will be followed until toxicities return to grade 1 or baseline as appropriate.

Addendum 5: Management of stomatitis/oral mucositis/mouth ulcers

Management of stomatitis / oral mucositis / mouth ulcers

Adverse Drug Reaction	Severity	Afinitor Dose Adjustment and Management Recommendations
Stomatitis	Grade 1 (Minimal symptoms, normal diet)	No dose adjustment required. Manage with non-alcoholic or salt water (0.9%) mouth wash severaltimes a day.
	Grade 2 (Symptomatic but can eat and swallow modified diet)	Temporary dose interruption until recovery to grade ≤ 1 . Re-initiate Afinitor at the same dose. If stomatitis recurs at grade 2, interrupt dose until recovery to grade ≤ 1 . Re-initiate Afinitor at a lower dose. Manage with topical analgesic mouth treatments (e.g. benzocaine, butyl aminobenzoate, tetracaine hydrochloride, menthol or phenol) with or without topical corticosteroids (i.e. triamcinolone oral paste)*.
	Grade 3 (Symptomatic and unable to adequately eat or hydrate orally)	Temporary dose interruption until recovery to grade ≤ 1 . Re-initiate Afinitor at lower dose. Manage with topical analgesic mouth treatments (i.e. benzocaine, butyl aminobenzoate, tetracaine hydrochloride, menthol or phenol) with or without topical corticosteroids (i.e. triamcinolone oral paste)*
	Grade 4 (Symptoms associated with life-threatening consequences)	Discontinue Afinitor and treat with appropriate medical therapy.

* using agents containing alcohol, hydrogen peroxide, iodine, and thyme derivatives in management of stomatitis as they may worsen mouth ulcers.

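### The adverse event definition has no grade threshold for laboratory values, so asymptomatic, untreated grade 3-4 values, most clearly lymphopenia, can be left out of the grade 3 or higher toxicity proportion

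*Combined protocol and SAP*

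**What the plan says.** Section 2.0 sets the yardstick: "Safety will be determined by the extent of avoidance of" CTCAE v4.0 toxicities of grade III or above. Section 6.0 (Sample size/Accrual Rate) rests the safety objective on the precision of that proportion: 60 patients, ±13%.

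Section 3.4.4 fixes the scale: "Toxicity will be scored using CTCAE Version 4.0 for toxicity and adverse event reporting". Section 3.4.4.1 fixes what is collected: "Information about adverse events that are grade 3 or above, whether volunteered by the subject" or found in other ways, laboratory tests included. The same section then limits which laboratory findings qualify. Abnormal "laboratory values or test results constitute adverse events only if they induce clinical signs or symptoms, are considered clinically significant, or require therapy". The second of these conditions is left to judgement, since under Section 3.4.4 "The investigator must appraise all abnormal laboratory results for their clinical significance". No threshold is given.

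Addendum 4 works from measured values. It lists specific hemoglobin, platelet and neutrophil limits under hematologic toxicity of grade III or above and attaches an action to each. For one cell line it attaches none: "No adjustments will be made for lymphopenia".

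**The concern.** The safety objective is expressed in CTCAE grades, and Addendum 4 assigns hematologic grades from the measured count. The adverse event definition applies a different test, in which grade plays no part. A value can therefore be grade 3 or 4 and still not be an adverse event. The only stated recording rule for grade 3 or higher findings is the one for adverse events, so such a value need not be recorded as a toxicity.

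This is a single-arm study whose primary objective is safety. If the headline proportion depends partly on whether the investigator calls an abnormal count significant, it may not be comparable between patients or over time, and any error runs in the favourable direction.

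**Working it through.** **Step 1. Reproduce the stated precision.** Inputs: N = 60 and ±13% (Section 6.0). The 95% level is the one Section 6.0 gives for its toxicity analysis, and p = 0.5 is the widest case.

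- Normal approximation: 1.96 × √(0.5 × 0.5 / 60) = 0.1265, or 12.7 points.
- Exact binomial for 30/60: 36.8% to 63.2%, a half-width of 13.2 points.

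Both agree with ±13%.

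**Step 2. Set the laboratory findings against the three conditions.**

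| Finding | Response in the protocol | Met without relying on judgement? |
|---|---|---|
| Hemoglobin below 8.0 g/dL | Red cell transfusion and hold (Addendum 4) | Yes, therapy |
| Grade 3 hyperglycemia or dyslipidemia | Interruption and medical therapy (Addendum 6) | Yes, therapy |
| Platelets below 10,000 | Platelet transfusion (Addendum 4) | Yes, therapy |
| Hepatitis B reactivation | Recorded as at least grade 3 (Addendum 9) | Yes, by its own rule |
| Platelets 10,000 to below 50,000; ANC below 1,000 | Hold only (Addendum 4) | Arguable: depends on whether a hold is therapy |
| Other non-hematologic laboratory values, grade 3 or above | Hold (Addendum 4) | Arguable, same reason |
| Lymphopenia, grade 3-4, asymptomatic | None (Addendum 4) | No |

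**Step 3. Direction and size.** Let L be the share of all patients whose only grade 3 or higher finding is a laboratory value, and u the share of those patients not recorded.

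Recorded proportion = true proportion − L × u

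Since L × u cannot be negative, the filter can only lower the proportion. The number of lost patients that equals the precision is 0.1265 × 60 = 7.6, so about 8 of 60 (8/60 = 13.3 points).

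The documents give neither L nor u. Purely as assumptions, take a true proportion of 50% and N = 60. Coverage is the probability that the exact 95% interval around the recorded figure contains the true 50%.

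| L | u = 25%: recorded (coverage) | u = 50% | u = 100% |
|---|---|---|---|
| 10% | 47.5% (96%) | 45% (92%) | 40% (74%) |
| 20% | 45% (92%) | 40% (74%) | 30% (16%) |
| 30% | 42.5% (85%) | 35% (44%) | 20% (0.2%) |

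The effect runs from negligible to severe, and nothing in the documents says which row or column applies.

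**Step 4. What the quoted rates can support.** For a previous everolimus lymphoma study of 37 patients, Section 1.1.3 reports: "The incidence of grade 3 anemia, neutropenia, and thrombocytopenia in this heavily pretreated patient population was 11%, 16%, and 30%, respectively". At N = 60 those rates would be 6.6, 9.6 and 18.0 patients, with unknown overlap. They show that laboratory-defined grade 3 events can be common. They do not estimate the loss: Step 2 shows that transfused anemia is captured and that hold-only cytopenias are arguable. Those patients also had a median of 4 prior therapies and took 10 mg daily, whereas dosing here is adjusted to a trough target. No lymphopenia rate is given.

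**The case against.** **A hold is treatment.** Section 3.4.4.1 itself names interruption and discontinuation of study drug among the ways an adverse event may be treated. On that reading a platelet or neutrophil count that forces a hold already requires therapy, and an investigator would hardly call it insignificant. This largely stands. A reader might infer that every hold-only cytopenia drops out, and the documents do not support that. What remains is ambiguity, because the sentence concerns events already classed as adverse events and nothing says that a mandated hold satisfies the definition. Lymphopenia is untouched by this argument.

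**The planned analysis uses other events.** A reader might infer that the stopping rule and the primary analysis are biased. They are not, at least directly: both count inability to tolerate the minimum dose, or unexpected hospitalization. This stands in full. That those events differ from the toxicity proportion in Section 2.0 and in the sample size paragraph is a separate matter to reconcile. It does not remove the proportion on which the trial is sized.

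**Toxicity is not the same as adverse event.** Section 3.4.4 lists hematology and chemistry monitoring beside adverse event recording, so the proportion might be meant to come from laboratory data. That is possible, but no section says so. If it is the intention, the fix merely writes it down.

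**Sites and frequency.** A reader might also expect recording to differ between sites, or these to be the protocol's most frequent toxicities overall. The documents describe one cancer center. Section 3.2.5 names decreased blood counts among the most frequent laboratory abnormalities, lists other events as the most frequent adverse events, and calls most events mild to moderate.

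**Conclusion.** The point holds in a limited form. As written, the adverse event definition lets asymptomatic, untreated grade 3-4 laboratory values be omitted at the investigator's discretion from the proportion that defines and sizes the safety objective. Lymphopenia is clearly exposed, hold-only values arguably so, and transfused anemia and treated metabolic events are not.

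The bias has a known direction, downward, and an unknown size. About 8 lost patients in 60 would equal the stated precision, but no particular loss can be claimed because L and u are assumptions. No decision threshold is attached to this proportion, so the consequence is an understated safety estimate and not a changed decision rule. The conclusion assumes that the proportion is built from recorded adverse events, the only recording rule the protocol gives for grade 3 or higher findings. The gap should be closed because safety is the primary objective and closing it is cheap.

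**What to change.** In Sections 3.4.4, 3.4.4.1 and 6.0, state that for the grade 3 or higher proportion, any on-treatment laboratory value that reaches CTCAE v4.0 grade 3 or higher and is worse than baseline is counted, whatever the symptoms, the significance judgement or the therapy given. Derive these grades from the scheduled CBC with differential, metabolic panel and lipid results. Report three proportions (laboratory-only, clinical and combined) and show lymphopenia separately so that it does not obscure the rest. The baseline condition matters because eligibility sets limits for platelets, hemoglobin and ANC but none for lymphocytes.

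The cost is protocol wording and some programming. No new tests, patients or changes in patient management are needed, and N = 60 with ±13% is unchanged. The reported proportion will be less favourable.
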